To the extent that logbooks or paper records for individual subjects need to be maintained for purposes of data collection or conducting the intervention, they will be kept locked in file cabinets in a locked room accessible to research staff only. All consent forms will be stored in the same manner. All data with subject identifiers will only be destroyed as soon as it is no longer needed for completion of study related activities.

References

57. Kline, R.B. (2011). *Principles and practice of structural equation modeling* (3rd ed.). New York, NY: Guilford Press.

Data Safety Monitoring Plan Appendix 1

Testing Protocols for HbA1C and Blood Pressure

Brief Hemoglobin HbA₁C and Blood Pressure Testing Protocol

1. Prior to Participant Appointment

- Turn on HbA1c machine – requires 8 minutes to warm up
- Open cartridge
 - Scan barcode
- Open NEW capillary pack
- Other supplies
 - Gloves
 - Alcohol wipes
 - NEW lancet

2. Take Blood Pressure Twice

- Decide which cuff to use for blood pressure and hook up to machine
- Place cuff on participant's upper arm with tubes coming down from midline
- Press start on the machine
- Record the measurement in the survey and on the participant's lab sheet
- Wait one minute and repeat previous steps to perform the second blood pressure reading on the same arm

***If BP > 180/120 → wait one minute and take second blood pressure reading.

If BP remains > 180/120 terminate interview and encourage to go to Urgent Care ***

If both readings, or only the second reading, are >180/120, terminate the interview and encourage to go to Urgent Care.

The >180/120 threshold was derived from the American Heart Association

NOTE: Both numbers do not need to meet 180/120. If systolic is above 180 OR diastolic is above 120, the participant should be encouraged to go to Urgent Care immediately. Provide list of nearby Urgent Care centers.

3. Finger Stick

- Ask participant if there is a finger they prefer to have poked
- Wipe fingertip with alcohol
- Put on gloves
- Poke fingertip with lancet
- Wipe off first drop of blood with gauze pad

4. Run DCA

- Suck blood up into capillary
- Insert capillary into cartridge
- Place cartridge inside the machine
- Pull foil tap out of cartridge while bracing it in the machine
- Close machine window

5. Clean Up

- Offer participant gauze to wipe off finger and band aid
- Remove gloves and discard in the biohazard bin
- Record HbA1C measurement in the survey and on the participant's lab sheet.
- Open HbA1c machine window, press down button, push cartridge to the right, & remove
- Dispose of cartridge, capillary (do not pull out plunger) and lancet in the sharps container
- Dispose of all other materials in the biohazard bin

Data Safety Monitoring Plan Appendix 1 Continued

Testing Protocols for HbA1C and Blood Pressure

Upper Arm Blood Pressure Detailed Testing Protocol**Preparation for the Blood Pressure Measurement:**

1. Ask participant to remove tight-fitting clothing or tight rolled up sleeve from their left upper arm.
2. Have the participant sit upright on a chair with their feet flat on the ground. The participant's arm should rest on a table so that the arm cuff is at the same level as their heart.
3. Ask the participant to remain still and refrain from speaking while the blood pressure measurement is taken.

Performing the Blood Pressure Measurement:

1. Insert the arm cuff air plug into the air jack, located on the left side of the automatic blood pressure machine.
2. Wrap the arm cuff firmly around the participant's left upper arm and secure the cuff using the fabric fastener.
 - a. The bottom edge of the arm cuff should be about $\frac{1}{2}$ inch above the elbow
 - b. The air tube attached to the arm cuff should be located inside the participant's arm and should align with their middle finger.
3. Press the START/STOP button located on the bottom right of the blood pressure machine's visual display. The arm cuff will start to inflate automatically.
 - a. The irregular heartbeat symbol will be displayed at the top of the display screen if the monitor detects an irregular rhythm two or more times during the measurement.
 - b. The movement error symbol will be displayed at the top of the display screen if the participant moves during the measurement. Remove the arm cuff and wait 2-3 minutes before attempting another measurement.
4. Record the participant's blood pressure
 - a. The blood pressure machine displays the systolic blood pressure above the diastolic blood pressure. The smaller number indicates the participant's pulse.
5. Once the arm cuff has completely deflated, remove the arm cuff and press the START/STOP button to turn the monitor off.
6. Record the measurement in the survey and on the participant's lab sheet.

Data Safety Monitoring Plan Appendix 1 Continued

Testing Protocols for HbA1C and Blood Pressure

Hemoglobin A_{1c} Detailed Testing Protocol

Materials Needed:

- Disposable Gloves
- Sharps/Biohazard Container
- Alcohol Wipes/Swabs
- HbA1c Machine
- Reagent Cartridge
- Capillary Holder
- Lancet Device
- Adhesive bandage
- Blue pad

[figure not shown]
Preparation for Hemoglobin A_{1c} Test:

1. Take out a new **reagent cartridge pack** from refrigerator for each new participant.
 - a. Remove Reagent Cartridge from its foil package and let sit for 5-10 minutes at room temperature
2. Turn power switch to On (I) position on the **HbA1c machine**. Allow approximately 8 minutes for the device to warm up.
3. Take out a new **capillary holder pack** and inspect that all materials are present and in good condition: absorbent pad, glass capillary and a properly working latching mechanism. A new capillary holder pack will be used for each new test.

Preforming Hemoglobin A_{1c} Test:

1. Put on disposable latex gloves.
2. Scan **reagent cartridge**. In a smooth, quick motion, slide the reagent cartridge down past the dot. A beep will sound to signal a successful scan has occurred.
3. Clean participant's fingertip with an **alcohol wipe**. Let dry.
4. Use a new **lancet device** to prick the participant's finger (see picture, right)
 - a. If necessary, squeeze fingertip until blood pools.
 - b. Wipe away first drop of blood. Re-squeeze fingertip if necessary
5. Hold the capillary holder at an angle and touch only the tip of the capillary to the small drop of blood on the finger until the capillary is filled.
 - a. Once the capillary is filled, the test must be performed within 5 minutes
 - b. Inspect the glass capillary for any air bubbles. If bubble(s) are present, repeat the procedure using a new capillary.
6. Carefully insert the capillary holder in the reagent cartridge until the holder snaps into place (see picture below).

Analyzing the Sample:

1. Make sure the HbA1c machine display reads "READY: SCAN BARCODE."

2. Hold the reagent cartridge so the barcode is facing right, insert the reagent cartridge above the dot on the barcode track, and slide cartridge down past dot until hear beep to signal successful scan has occurred.
3. Open the cartridge door of the machine and insert the reagent cartridge with the barcode facing right into the compartment until a subtle snap is heard/felt.
4. In a smooth, quick motion, pull the flexible pull-tab out of the reagent cartridge.
5. Close the cartridge door. Within 5 seconds, a beep should sound indicating the assay is in progress.
 - a. *The test takes approximately 7 minutes to complete.*
6. Results will show up on the display.
7. Record the measurement in the survey and on the participant's lab sheet.

Removing the Reagent Cartridge:

1. Open cartridge door.
2. Locate the button on the right side of cartridge door. Push and hold it down with your right hand.
3. With your left hand, gently push the tab on the cartridge to the right. This action releases and unlocks the cartridge.
4. Pull the reagent cartridge out of the compartment.
5. Discard the reagent cartridge in the proper container, according to standard operating procedures.

*****Be sure to dispose of all sharps (lancets) and biohazardous materials (capillary & cartridge) in the appropriate disposal containers*****

Data Safety Monitoring Plan Appendix 2

We will follow the guidelines for classifying Adverse Events and the timeline for reporting Adverse Events as outlined by the University of Michigan Medical School Office of Research found here: <https://az.research.umich.edu/medschool/guidance/adverse-event-reporting> and in accordance with the study DSMP.

We will follow the Adverse Events, Other Reportable Information and Occurrences, & Other Required Reporting guidelines outlined by the University of Michigan Medical School Office of Research found here: <https://az.research.umich.edu/medschool/guidance/adverse-events-aes-other-reportable-information-and-occurrences-orios-other> and here <https://az.research.umich.edu/medschool/guidance/adverse-events-aes-other-reportable-information-and-occurrences-orios-other> and in accordance with the study DSMP.

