4.1 Inclusion and Exclusion Criteria

Study participants will meet the following criteria:

- 18-75 years of age
- Have access to a telephone that can receive and send text messages
- diagnosis of diabetes with prescribed anti-hyperglycemic medication
- most recent (within the past 6 months) recorded hemoglobin A1c (HbA1c) level of $\geq 7.5\%$ for individuals ≤ 70 years and $>8.0\%$ for individuals between 70-75 years in age
- positive report of financial burden or CRN using screening questions developed and validated from prior work³³⁻³⁷

Exclusion criteria include significant cognitive impairment precluding individuals from completing the study as evidenced by ability to complete study intake procedures and current participation in another diabetes study.

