4.2 Source of Participants

We will recruit potential participants from the University of Michigan's Diabetes Research Registry and the University of Michigan Medical School Office of Research DataDirect. The Diabetes Research Registry and DataDirect meet HIPAA security and privacy requirements and provide streamlined access to potential participants' electronic health records (EHR). The study team will be accessing participants' electronic health records (EHR) via the Diabetes Research Registry and the University of Michigan Medical School Office of Research DataDirect. Over 6,000 (18–75 years) diabetes patients are included in the registry and receive care at the University of Michigan's ambulatory care clinics. Thirty percent of registrants have type 1 diabetes, and 70% have type 2 diabetes, with equal proportions of men (49.6%) and women (50.4%). Mean age is 54.3 ± 15.9 years, mean duration of diabetes is 15.8 ± 11.2 years, and 30% of registrants are racial/ethnic minorities.⁴⁶ Registrants tend to have many complications and comorbidities, thus an ideal population for the proposed study. As of January 2017, the proportion of adult patients in the Diabetes Research Registry with an HbA1c test ≤ 7 was only 24%, and the proportion with HbA1c ≥ 9 was 24%. From our pilot study in the same health system, 77% of individuals approached and interested in participating reported either financial burden with their diabetes treatments or engaging in a CRN behavior, 47% reported a household income <\$40,000/year, and 37% were unemployed. Based on these data and the high retention in our pilot study at follow-up (94%), the Diabetes Research Registry will provide an adequate recruitment pool of at least 1,500 eligible participants to achieve our recruitment and retention goals.

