Appendix 2: Participation Flowchart

Appendix 3: CareAvenue Intervention Website Overview Diagram

Appendix 4: Data Safety Monitoring Plan

Data and Safety Monitoring Plan

NIH Study Number: 1 R01 DK116715-01A1

Title: Improving diabetes outcomes and health disparities through a patient activation intervention addressing unmet resource needs

Principal Investigator: [name], MPH

I. Overview

A. Study Purpose

The purpose of this study is to determine the extent to which activating diabetes patients to address health-related financial burdens that impact treatment adherence and unmet social risk factors improves disease control, and the mechanisms through which primary and secondary outcomes are achieved. The goal of this study is to evaluate CareAvenue on health outcomes- an automated, e-health screening, feedback and skills training intervention that addresses health-related financial burden and unmet SDHs.

B. Adherence Statement

The Data and Safety Monitoring Plan (DSMP) outlined below for (1 R01 DK116715-01A1) will adhere to the protocol approved by the University of Michigan Institutional Review Board (IRBMED), National Institute of Diabetes and Digestive and Kidney Disease (NIDDK), and the study Data Safety Monitoring Board (DSMB).

C. Data and Safety Monitoring Board (DSMB)

The purpose of the study DSMB is to monitor the safety and conduct of the study. The responsibilities of the DSMB are outlined in the charter.

II. Adverse Events, Other Reportable Incidents and Occurrences, and Unanticipated Problems

A. Assessment of Participant Risks

Potential risks for this study include:

- A common side effect of the finger stick blood draw is localized discomfort or bruising
- In rare cases, infection may occur as a result of the capillary blood collection
- In rare cases, fainting may occur as a result of the capillary blood collection

Discomfort, bruising, fainting, infection, or any other unexpected adverse reactions to the capillary blood collection will be documented. All identified risks are addressed in the study protocol and have been outlined in the study consent form.

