All research staff will undergo training in line with university and federal guidelines. Staff of the University of Michigan Department of Pathology will thoroughly train research staff on taking HbA1c assessment using established protocols that emphasize sanitation, cleaning the site of the prick with alcohol before and after, and properly disposing of gloves and fingersticks after each assessment. Once trained, research staff can train additional staff on use of the HbA1c machine. All research staff will undergo Biosafety Training for Laboratory Personnel offered by the University of Michigan Institutional Biosafety Committee. First aid will be available onsite at the location of testing. Study HbA1C testing protocols can be found in Appendix 1.

i. Adverse Events

Adverse Events (AEs) are events that involve physiological, social, economic, or psychological harm to subjects. They may include symptoms, abnormal test results, a response to the study procedures, or any combination of these. Adverse events may also indicate risks of harm to other

subjects or others who are not study subjects but may be affected directly or indirectly. AEs include harmful effects that are both expected and unexpected.

The study will rely on self-reporting by study participants of adverse events. All participants will be provided with contact information for the project manager and study PI. Both in the study consent form and through verbal instructions from data collection staff, participants will be instructed to contact the project manager and PI if they experience any of the expected potential adverse events or experience any other events, symptoms, or occurrences that are unusual for them to experience whether they believe they are related to the study or not. Additionally, the study team will formally assess for Adverse Events/Serious Adverse Events at the Follow-up 1 (6 months-post baseline) and Follow-up 2 (12-months post baseline) data collection time points. The study team will utilize case report forms to collect this information from participants. Specific safety data the study team will assess includes:

- Discomfort, bruising, infection, fainting or unexpected adverse reactions to the capillary blood collection for the HbA1c measurement

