- Negative outcomes related to use of the CareAvenue website (intervention group), Guest Assistance Program services (control group), receiving IVR calls (intervention group), or receiving text messages (intervention and control groups). This includes participant concerns related to privacy and safety of their information.
- Events resulting in inpatient hospitalization, prolongation of existing hospitalization, or emergency department visits
- Death (reported to the study team by an individual acquainted with the participant)
- Other non-specified events the participant shares

In addition to self-reporting, all data collectors will be instructed to report any indicators of adverse events to the project manager as soon as possible and not more than by the end of the business day. Indicators of adverse events may be observations of study subjects during data collection or reports made by study subjects directly to data collectors during routine study contact. Once the event has been reported to the project Manager, the project Manager will inform the PI. The PI will review the event and make a determination on the expectedness and relatedness of the event to the study using the University of Michigan Medical School Office of Research guidelines (see Appendix 2). This will occur within 24 hours of the initial report of the adverse event.

ii. Other Reportable Incidents and Occurrences

Other Reportable Incidents and Occurrences (ORIOs) are events in which no one suffered actual harm but indicate that there is a potential for future adverse events to occur. This includes events that may increase risk, alter the risk-benefit assessment, affect a participant's willingness to participate in the study or any departure from the human subject protection regulations and policies set forth by the IRB, NIDDK, or in this DSMP.

iii. Unanticipated Problems

Unanticipated Problems (UaPs) are events that are unexpected, related or possibly related to the study, and suggests that participation in the study places the participant or others at a greater risk of harm than was previously thought. Unanticipated problems do not include events in which harm has already occurred (which would be classified as an adverse event) or events in which potential harm or risk to subjects occurs (which would be classified as an ORIO). UaPs may happen to participants or non-participants who are affected by a person taking part in the study.

B. AE reporting

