 - b. Non-serious UaPs will be reported within 14 calendar days.
3. All serious and non-serious UaPs will be reported to the DSMB within one week of reporting to the IRB.
4. Any action resulting in a temporary or permanent suspension of this study, such as actions by IRBMed, the study DSMB, or investigators, will be immediately reported to the appropriate NIDDK program official.

III. Safety Review Plan and Monitoring

Oversight of subject safety includes review of adverse events as well as study progress, data integrity and study outcomes.

A. Justification of sample size

We propose to enroll 600 subjects in this study. The hypothesis to be tested is that the intervention will lead to uptake of low-cost resources for health and unmet basic needs and reductions in CRN, thus leading to medication/regimen adherence and intensification. We expect the beneficial impacts from improved access to treatment recommendations and unmet basic needs can lead to improved HbA1c

management and control. A 0.5 or greater reduction in HbA1c, after adjusting for confounding covariates, is considered a clinically meaningful change in stabilizing or improving HbA1c control.¹ We designed the study to have 80% power at an alpha level of 0.05 to detect a change difference of 0.53 unit change in hemoglobin HbA1c between study arms, and a standard deviation of 1.46 based on early data collected in the study.² We will need a total of 510 subjects (255 per arm) with outcome data to show a 0.53 unit difference in HbA1c. With this sample size, we will also have sufficient power to detect differences in our other self-reported secondary outcomes.

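### The plan expects more glucose-lowering treatment to be taken but does not specifically ask about hypoglycaemia, so episodes managed at home are incompletely ascertained

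*Combined protocol and SAP*

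**What the plan says.** **Mechanism.** Protocol section 10 and DSMP III.A give the same causal chain: uptake of low-cost resources and "reductions in CRN, thus leading to medication/regimen adherence and intensification", and through these better HbA1c.

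**Population.** Section 4.1 requires a "diagnosis of diabetes with prescribed anti-hyperglycemic medication" and a positive screen for financial burden or cost-related non-adherence. Section 4.2 describes the main source registry: "Thirty percent of registrants have type 1 diabetes, and 70% have type 2 diabetes", with a mean diabetes duration of 15.8 years.

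**Named risks.** Protocol section 3.1 lists breach of confidentiality and finger-stick risks. The DSMP II.A list is confined to the finger stick and begins "A common side effect of the finger stick blood draw is localized discomfort or bruising".

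**Solicited safety data.** DSMP II.A.i provides for formal adverse event assessment on case report forms at 6 and 12 months. The five listed items are:
1. "Discomfort, bruising, infection, fainting or unexpected adverse reactions to the capillary blood collection for the HbA1c measurement";
2. negative outcomes of using the website, the Guest Assistance Program, the automated (IVR) calls or the text messages;
3. "Events resulting in inpatient hospitalization, prolongation of existing hospitalization, or emergency department visits";
4. death;
5. an open item for anything else the participant mentions.

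**Spontaneous reports.** The same section tells participants, in the consent form and verbally, to report events that are unusual for them, whether or not they think the study is the cause.

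**The concern.** Participants enter because cost is a burden or already limits what they take. If the intervention does what the plan hopes, some will take more of a prescribed glucose-lowering regimen, and some regimens will be stepped up. Low blood glucose is the physiological harm one would look for first under that mechanism, and the supplied text does not mention it.

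The Data and Safety Monitoring Board (DSMB) is charged with weighing risk against benefit. For low-glucose episodes that do not reach a hospital or emergency department, it would be working from whatever participants chose to mention. Such counts are likely to be too low. They may also be too low by different amounts in the two arms, which would make a comparison by arm hard to read.

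**Working it through.** There is no plan figure to reproduce. The check is whether any route in the text would record a low-glucose episode treated at home, for example one where a family member had to help.

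**Step 1: the five solicited items.**

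| Item (DSMP II.A.i) | Would it record a home-managed episode? |
|---|---|
| Finger-stick reactions | No. Fainting is listed, but only as a reaction to the blood collection. |
| Negative outcomes of study components | Only if the participant links the episode to the website, the assistance program, the calls or the texts. |
| Hospital or emergency department events | No, by setting. It does record episodes treated there. |
| Death | No, unless fatal. |
| Open final item | Only if volunteered. |

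Items naming hypoglycaemia: 0 of 5.

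**Step 2: spontaneous reporting.** Attribution to the study is not required, so this route is open in principle. The limit is the word unusual. In a registry population with a mean diabetes duration of 15.8 years, a low may be familiar and so fall outside the instruction as a participant hears it.

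**Step 3: everywhere else.** Hypoglycaemia is absent from the risks (section 3.1; DSMP II.A), the outcomes (section 6.4, Table 2), the DSMB guidelines for action (DSMP III.C) and the supplied DSMB charter text.

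**Step 4: recall.** Formal assessment happens twice. With the visit windows in section 6.1, the longest interval between the two follow-ups is (12 months + 4 weeks) − (6 months − 2 weeks) = 6 months + 6 weeks. An unprompted event has to be remembered over that span.

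**Step 5: comparability of arms.** Section 6.3.2 gives the scheduled text contact over 52 weeks:
- intervention: 4 to 5 per week, 4 × 52 = 208 to 5 × 52 = 260 messages, plus automated (IVR) calls;
- control: 3 to 4 per week, 3 × 52 = 156 to 4 × 52 = 208 messages, with no such calls.

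Part of solicited item 2 is also arm-specific. What participants volunteer may depend on how much contact they have had and what they have been prompted about. The text does not allow the direction or size of that difference to be predicted.

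**The case against.** The strongest reply is that this is an information-based behavioural trial with broad adverse event capture and a DSMB, and that the study itself neither doses nor titrates anything. Much of that stands. It rules out several stronger readings that a reader might infer:

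- *That the plan cannot see hypoglycaemia at all.* Episodes leading to hospital or emergency care are solicited, and DSMP II.B requires a description of every reported event, related or not.
- *That participants would have to blame the study.* The reporting instruction expressly removes that condition.
- *That the DSMB could not see a difference by arm.* The charter puts adverse events before it by masked group, with unmasking on request. What it would lack is complete ascertainment of home-managed episodes.
- *That the risk rises in the intervention arm alone.* Section 10 anticipates spillover to controls, who also receive diabetes-management texts and assistance program details. Better food access could even reduce lows.
- *That an HbA1c unmasking criterion looking only at increases (DSMP III.C) is a defect.* A fall is the intended benefit, and a three-month average does not count low-glucose episodes.

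A further reply is that the forms may already ask. DSMP II.A.i describes a list of specific safety data, not the form itself, and neither the case report forms nor the surveys are among the documents. This cannot be excluded. If the question exists, the DSMP should list it.

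What the reply does not answer is that a harm following from the plan's own mechanism depends on volunteering whenever it is managed outside hospital.

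**Conclusion.** The point holds as incomplete, and possibly unequal, ascertainment: hypoglycaemia is not specifically solicited in the supplied protocol and DSMP text. Episodes treated in hospital or an emergency department are captured; those managed at home are captured only if volunteered.

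The size is qualitative. None of the five solicited items names the event, and the documents give neither a hypoglycaemia rate nor the share of episodes reaching hospital. A reader might want to project the number of missed episodes from the registry's 30% type 1 share. The documents do not support that: the share describes the registry, whereas the trial sample is filtered by HbA1c and financial burden and drawn partly from DataDirect.

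The conclusion rests on two assumptions: that the unseen forms and surveys contain no such question, and that some participants would not regard a low as unusual. This is an inexpensive improvement to safety data. It is not a contradiction in the plan and does not threaten the primary analysis.

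**What to change.** 1. Add one fixed item to the adverse event case report form at Follow-up 1 and Follow-up 2, worded identically in both arms: any low-blood-sugar episodes since the last assessment that needed another person's help (yes/no, and how many), whether or not thought related to the study.
2. Tabulate it by masked arm in the closed-session report, with the number of participants asked.
3. Add low blood sugar to the DSMP II.A risk list, so that the expectedness ruling and the annual comparison with anticipated adverse event rates have something to refer to.
4. If the existing forms or surveys already ask this, list the item in DSMP II.A.i and make only changes 2 and 3.

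The cost is about a minute of interview time at each follow-up, one table row and an IRB amendment. Recall over roughly six months will be imperfect, but the same prompt in both arms gives a more comparable count than volunteered reports. The change concerns data collection only and alters no treatment or clinical rule.
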